National collaborators from 12 regions in Sweden, 23 hospitals, have already agreed to participate in this multicenter study. Stockholm region: Karolinska University Hospital Solna and Huddinge, Danderyd Hospital, Stockholm South General Hospital, Södertälje and Norrtälje Hospital. Uppsala region: Uppsala University Hospital. Östergötland region: Linköping University Hospital. Gotland region: Visby lasarett. Skåne region: Skåne University Hospital in Lund and in Malmö. Halland region: Kungsbacka Hospital. Västra Götalands region: Sahlgrenska University Hospital, Östra Hospital, Kungälv Hospital. Värmland region:

Karlstad Central Hospital. Gävleborg Region: Gävle and Bollnäs Hospital. Västerbotten region: University Hospital Umeå. Örebro: University Hospital Örebro, Karlskoga lasarett, Lindesberg lasarett. Jönköping region: Eksjö Hospital.

International collaborators from Rizzoli hospital in Bologna, Italy have shown interest to participate.

Estimated sample size and power

We plan to include at least 1400 patients, with 10% drop-out accounted for, although our earlier study demonstrated a 5.3% drop-out⁹. Many patients will in clinical routine receive LMWH, which is accounted for. This gives the trial 90% power (alpha 0.05) to identify an absolute risk reduction of 8% (28% vs. 20%) and relative risk reduction of 29% in primary outcome. The expected relative risk reduction is higher, 40%, and the minimum clinical relevant absolute risk reduction in primary outcome between the groups is 4% based on recent studies^{9,26}.

The frequency of our primary outcome is given from recent studies showing a 50% rate of CDU-verified DVTs after ATR and 25% rate after ankle fracture (AF)^{9,27}. This gives a total DVT-rate of 33% when including two AF for every ATR. As extra precautions we reduced the expected total DVT-rate from 33% to 28% and reduced the relative risk reduction from 40% to 30%.

The 1400 included patients will consist of at least 400 ATR- and at least 1000 AF-patients, with the same drop out as above. For subgroup analyses (ATR / AF) this gives the trial 80% power (alpha 0.05) to detect a 30% relative risk reduction and an absolute risk reduction of 8% (25% vs. 17%) for AF and 15% (50% vs. 35%) for ATR in primary outcome.

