The randomisation form should be filed in the patient's medical notes, along with one copy of the signed informed consent form and patient brochure. The patient should receive a patient brochure along with a signed copy of the consent form. Copies should also be kept in the site file. The treatment allocation will be blinded for the assessors of outcome; i.e. ultrasonographers doing the CDU, physiotherapists or nurses performing the patient reported outcomes. The IPC-therapy will, due to its nature, not be blinded to the patient and the clinician applying the therapy.

Statistical analysis plan ([name], statistician)

All analyses will be based on intention to treat. We will analyze patients in the groups they are randomized to, regardless of treatment received. A patient might be withdrawn because of severe non-adherence or withdrawal of consent by the patient. For binary outcomes (e.g. occurrence of a primary or secondary outcome OR not), outcomes will be presented as odds ratios and 95% confidence intervals, adjusted using logistic regression for the factors used in the minimization algorithm and weight-bearing. We will calculate absolute reductions in risk from these values, as presented in the reference with similar study design²⁶.

Group differences for ordinal secondary outcome data, such as the patient-reported data (ATRS and OMAS), will be analyzed by nonparametric tests²⁰. Group differences for EQ5D-5L (index scale), FAOS (ratio scale) and continuous secondary outcome data will be analyzed by t-tests if the data are normally distributed, and using an appropriate nonparametric test otherwise.

Subgroup analyses will be performed to determine whether certain types of patients might gain greater or less benefit from IPC. We will estimate the effect of treatment allocation on the primary outcome subdivided by key baseline variables and adjusted for the other factors included in the minimization algorithm. Subgroup analyses will be performed by observing the change in log-likelihood when the interaction between the treatment and the subgroup is added into a logistic regression model. We will determine whether there is significant heterogeneity between these subgroups. The following preplanned subgroup analyses will be performed:

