Is IPC more effective in patients at higher risk of DVT? It seems likely that patients at higher risk of DVT might gain greater benefit from IPC than those at lower risk. Patients with ATR exhibit higher risk of DVT than patients with AF, and patients aged ≥ 40 years exhibit almost fivefold higher odds of developing DVT⁹. Moreover, prior history of DVT, weight-bearing, and surgery are likely to affect the risk of DVT. Therefore, we will undertake subgroup analyses of the effect of allocation to IPC on the primary outcome among patients with and without at least one of these factors at baseline.

Analysis of impact of delay in applying IPC? There is often a delay in presenting or being treated with a lower limb injury (ATR/AF) and therefore this can lead to a delay in applying VTE prophylaxis. Moreover, patients may even suffer a VTE before treatment is initiated. Thus, we hypothesize that IPC will reduce the frequency of the primary outcome to a greater

extent among patients enrolled early compared to later. We will therefore examine the effect of treatment among patients enrolled early versus later after injury.

Compliance and duration of treatment with IPC? IPC compliance was 91% in our recent trial, but has usually been used for a relatively short time on perioperative patients and in outpatients. There is a concern that IPC may not be used for the whole six weeks or that it will not be applied continuously. We will therefore carry out additional analyses in order to determine how IPC-compliance affects the primary outcome.

Economic analyses: Economic analysis of the trial treatment effects will involve a within-trial evaluation of cost effectiveness integrated into a decision-analytic model of longer run costs and health effects. The within-trial analysis will be conducted on an intention-to-treat basis. The primary health endpoints will be VTE times adjusted for patient reported outcome.

A societal perspective will be taken for assessing costs of patient's care during the six-week immobilization. Patient-specific hospital resource use will be measured. The net direct medical cost will include a cost estimate of IPC capital/equipment (and staffing implications) and the averted costs arising from the effects of IPC on expected DVT/PE incidence. Probabilistic sensitivity analysis will also be used to assess the hospital cost distributions.

Specific intermediate objectives

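### The greater-benefit question for higher-risk patients has only a log-odds interaction test; the matching contrast in absolute risk reduction, with a confidence interval, is not planned

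*Combined protocol and SAP*

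**What the plan says.** The subsection of the statistical analysis plan on patients at higher risk of DVT states the expectation: "It seems likely that patients at higher risk of DVT might gain greater benefit from IPC than those at lower risk". It names injury type first ("Patients with ATR exhibit higher risk of DVT than patients with AF"), then age, prior DVT, weight-bearing and surgery. The comparison it plans is "among patients with and without at least one of these factors at baseline". No effect scale is given for benefit.

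The general part of the *Statistical analysis plan* gives one method for all subgroup questions: "observing the change in log-likelihood when the interaction between the treatment and the subgroup is added into a logistic regression model". The decision step is "We will determine whether there is significant heterogeneity between these subgroups". The treatment effect is also to be estimated within subgroups.

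For binary outcomes in general, "outcomes will be presented as odds ratios and 95% confidence intervals, adjusted using logistic regression", followed by "We will calculate absolute reductions in risk from these values". That sentence precedes the subgroup paragraph and does not refer to it.

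*Estimated sample size and power* states: "For subgroup analyses (ATR / AF) this gives the trial 80% power (alpha 0.05) to detect a 30% relative risk reduction". The rates it attaches are 25% versus 17% for AF and 50% versus 35% for ATR.

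**The concern.** The question is about benefit, and the test is about odds ratios. When two groups have different baseline risks and a similar relative effect, the higher-risk group has the larger absolute gain, while the log-odds interaction is close to zero. The planned test can therefore come out null when absolute benefit differs substantially. The plan's own figures describe this situation: nearly the same relative reduction in both injuries, and almost twice the absolute reduction in ATR.

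At stake is how a supplementary result is read. The protocol wants the trial to inform guidelines, and the absolute reduction by risk group bears directly on whom to offer IPC. As written, the only formal answer to the greater-benefit question would be a p-value on another scale, with no interval for the difference in absolute reduction.

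**Working it through.** **Inputs.** From *Estimated sample size and power*: at least 400 ATR and 1000 AF patients; 10% drop-out; alpha 0.05; rates 50% vs 35% (ATR) and 25% vs 17% (AF). From *Study Design*: 1:1 allocation. Sidedness is not stated; two-sided is assumed. After drop-out this leaves 180 per arm for ATR and 450 per arm for AF. Calculations are unadjusted.

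**1. The plan's own 80%.** Within-injury power = Φ[(d − 1.96·s₀)/s₁], where s₀ is the pooled and s₁ the unpooled standard error of the risk difference d.

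- ATR: (0.15 − 1.96 × 0.0521)/0.0515 = 0.93, power 82.4%.
- AF: (0.08 − 1.96 × 0.0272)/0.0270 = 0.99, power 83.9%.

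With a continuity correction the values are about 79% and 82%. The stated 80% therefore reproduces, as power for the effect within each injury.

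**2. The planned interaction, log-odds scale.**

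- OR in ATR = (0.35/0.65)/(0.50/0.50) = 0.538
- OR in AF = (0.17/0.83)/(0.25/0.75) = 0.614
- Ratio = 0.538/0.614 = 0.876; log = −0.132
- SE = √Σ 1/[n·p(1−p)] over the four cells = √(0.0222 + 0.0244 + 0.0119 + 0.0158) = √0.0742 = 0.272
- |z| = 0.132/0.272 = 0.48; two-sided power 7.7%

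Simulating the likelihood-ratio test that the plan names (3000 runs) gave 8.2%. The false-positive rate is 5%.

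**3. The same contrast on the absolute scale.**

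- ATR 0.50 − 0.35 = 0.15; AF 0.25 − 0.17 = 0.08; ratio 15/8 = 1.88; difference 0.07
- SE = √Σ p(1−p)/n = √(0.00139 + 0.00126 + 0.00042 + 0.00031) = √0.00338 = 0.058
- z = 0.07/0.058 = 1.20; power 22.5%
- Expected 95% CI: 7 ± 1.96 × 5.8, about −4 to +18 points

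**4. Sensitivity to the assumed effect** (180 and 450 per arm).

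| Scenario | Ratio of ORs | Power, log-odds | Absolute difference | Power, absolute |
|---|---|---|---|---|
| Stated rates | 0.88 | 8% | 7 points | 23% |
| Exact 30% relative reduction (AF 25% vs 17.5%) | 0.85 | 9% | 7.5 points | 25% |
| 40% relative reduction (50% vs 30%, 25% vs 15%) | 0.81 | 12% | 10 points | 42% |

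The last row uses the relative reduction that the protocol says it expects before its precautionary lowering.

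**5. What cannot be computed.** The higher-risk subsection groups patients by presence of at least one listed factor. The documents give neither event rates nor prevalence for that grouping, so the power of that contrast is unknown. ATR versus AF illustrates the effect of scale.

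**The case against.** Six objections have force.

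- *The absolute scale is already in the plan.* Partly true: the plan will calculate absolute reductions for binary outcomes and will estimate effects by subgroup. What is missing is the link between the two, and any contrast with an interval.
- *The test behaves correctly.* It does. The planning rates assume nearly one relative effect, so a test of relative heterogeneity should find little. A likelihood-ratio interaction test is standard and should stay. It simply does not answer whether absolute benefit differs.
- *An absolute-scale test would also usually be non-significant.* Correct: at the stated rates it would miss about 77% of the time. The reason for the addition is the estimate and its interval, which show what the data can and cannot exclude.
- *The 8% is not the power of the planned composite contrast.* Correct; it is an illustration.
- *A reader might infer that the trial will declare equal benefit when the interaction is non-significant.* The documents do not support this. They say only that significance of heterogeneity will be determined, and no rule for reading a null result is given.
- *A reader might infer that the 80% subgroup power is wrong, or is claimed for the heterogeneity test.* Neither is supported. The sentence lists within-injury effects and the figure is right for them. A label would be an optional clarification.

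**Conclusion.** The point holds as a gap between question and analysis in a supplementary part of the plan. The only heterogeneity assessment is on the log-odds scale, and no between-subgroup contrast or interval is planned for absolute reductions. At the plan's ATR and AF rates, a 1.9-fold difference in absolute benefit corresponds to a ratio of odds ratios of 0.88 and about 8% power, rising to about 12% at a 40% relative reduction. These figures assume a two-sided 0.05 level, 10% drop-out, no covariate adjustment, and ATR versus AF as the contrast.

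The finding does not extend to the primary analysis, and changing scale would not make this a well-powered comparison.

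**What to change.** In the *Statistical analysis plan*:

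1. Keep the likelihood-ratio test and label it the test of relative (odds-ratio) heterogeneity.
2. For each preplanned subgroup, estimate the absolute risk reduction in each level by standardisation from the same interaction model. Report the difference between levels with a delta-method or bootstrap 95% CI, and name this as the answer to the greater-benefit question.
3. State that a non-significant log-odds interaction will not be read as equal absolute benefit, and that the absolute contrast is presented as an estimate with its CI, not as a decisive test (for ATR versus AF, SE about 5.8 points and power about 23% at the planning rates).
4. Optionally, in *Estimated sample size and power*, label the 80% as power for the effect within each injury.

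The cost is a few sentences and a few lines of code on a model already planned. No new data or patients are needed.

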The mean inclusion per hospital is (one)-two AF each week and one ATR every second week, which totals at least a mean of 75 patients/hospital/year⁹. With 1,5 patients included per week per each hospital (20 hospitals registered), we will finish inclusion within one year.

For the secondary patient-reported outcomes, the trial has more than 95% power (alpha 0.05) to identify a clinically relevant difference, which at one year is 10 points difference on the rating scales (0-100)²⁰. For the explanatory VTE-preventive mechanisms (blood serum test) and collagen production (microdialysis) earlier studies demonstrate that a sample size of 100 gives 90% power to detect significant differences between groups, which will save expenses.

Treatment compliance of the patients, which was 91% in our earlier study, will be registered both by the IPC-device and by the patient. Patients will daily register the number of hours that IPC was used.

Material: Patient selection – population, sample

Male and female patients aged between 18 and 75 years with an acute injury requiring lower-leg immobilization, i.e. acute unilateral ATR or isolated AF, in a hospital setting will be eligible. The exclusion criteria will be: inability to give informed consent; planned follow-up at another hospital; renal failure; heart failure with pitting oedema; thrombophlebitis; malignancy; peripheral vascular disease; haemophilia/thrombophilia and pregnancy⁹.

The randomising clinician or nurse will screen for eligible patients as soon after their presentation to hospital as possible. To minimize differences between hospitals, patients will be eligible for inclusion if treatment starts within 10 days after the injury. IPC-prophylaxis for

DVT may have greater effect if started early after injury, but these potential differences will also be considered below. The responsible clinician collects the baseline data necessary to complete a randomization form. He/she then will randomize patients via a central, web-based service (RedCap) by giving the baseline data (which are then stored securely) and receives the treatment allocation at the end of the session.

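### The delay analysis splits enrolment into early and later with no cut-point; days from injury to randomisation, kept continuous, would use more of the data and leave no cut to choose

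*Combined protocol and SAP*

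**What the plan says.** In the section on patient selection, the protocol states that "patients will be eligible for inclusion if treatment starts within 10 days after the injury". It concedes that IPC prophylaxis "may have greater effect if started early after injury, but these potential differences will also be considered below". The only later text on timing is in the statistical analysis plan, under the question on the impact of delay in applying IPC. That paragraph gives the hypothesis that "IPC will reduce the frequency of the primary outcome to a greater" extent in patients enrolled early, and says the investigators will "examine the effect of treatment among patients enrolled early versus later after injury".

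The general method for subgroups stands just before it. The plan will estimate the "effect of treatment allocation on the primary outcome subdivided by key baseline variables" and test heterogeneity by "observing the change in log-likelihood when the interaction between the treatment and the subgroup is added into a logistic regression model". The list is introduced with "The following preplanned subgroup analyses will be performed". So the test is specified, but the grouping for delay is not. By contrast, the same part of the plan gives an age threshold of 40 years when it discusses risk factors. The minimisation factors are not listed, so they supply no cut for delay either.

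The two places also count time to different events: the eligibility rule to the start of treatment, the delay analysis to enrolment.

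**The concern.** Two things follow from an unspecified split.

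First, grouping treats all patients on one side of the cut as alike. If the benefit falls steadily as IPC starts later, the differences within each group carry information that the split throws away, and the interaction test loses power.

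Secondly, the window allows several whole-day cuts. A test that is nominally at 5% keeps that level only if the cut is fixed without reference to the outcomes.

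The trial is meant to inform guidelines on IPC during immobilisation, and this is the only planned analysis of timing. A spurious delay effect, or a real one missed, could influence how the results are read for patients who present late.

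**Working it through.** **Inputs from the protocol (sample size section and study design).** At least 1400 patients, 10% drop-out, 1:1 allocation, 28% vs 20%, 90% power, alpha 0.05 (taken as two-sided). Evaluable: 1400 × 0.90 = 1260, or 630 per arm.

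**Step 1: the plan's own figure.** The documents give no figure for the delay analysis, so the check starts from the main sample size. With mean rate 0.24, n per arm = [1.96 × √(2 × 0.24 × 0.76) + 1.2816 × √(0.28 × 0.72 + 0.20 × 0.80)]² / 0.08² ≈ 597. Then 2 × 597 / 0.90 ≈ 1327. With a continuity correction it is 622 per arm, and 1244 / 0.90 ≈ 1383. Power with 630 per arm is 91.5%. The stated 1400 and 90% are reproduced closely enough to use as the basis below.

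**Step 2: assumed delays.** The documents give no delay distribution. Three were assumed on whole days 0 to 10: uniform, and two weighted to early days (each day's weight 0.7 or 0.5 times that of the day before).

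**Step 3: information kept by a split.** For a linear trend this is the squared correlation between day and the early/later indicator, that is, between-group variance over total variance. The uniform case can be done by hand. Days 0–4 and 5–10 have means 2 and 7.5. Between-group variance is (5/11)(6/11)(7.5 − 2)² = 7.5, total variance is 10, and the ratio is 75%.

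**Step 4: power.** The planned likelihood-ratio interaction test was simulated without covariates (1260 patients, 2000 trials per distribution), with the log odds ratio changing linearly with delay. The slope was set to give exact days roughly 80% power: 2.8 × SE / SD of delay, where SE = √[1/(630 × 0.28 × 0.72) + 1/(630 × 0.20 × 0.80)] = 0.133. For uniform delay this is 2.8 × 0.133 / 3.16 = 0.118, a ratio of odds ratios of 1.125 per day. For the early-weighted cases it is 1.176 and 1.307 per day.

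**Step 5: false positives.** The same test with no true delay effect (4000 trials per distribution) was run with exact days, with one near-median cut fixed in advance, and with the most significant of all whole-day cuts leaving at least 10% of patients on each side (8, 5 and 3 such cuts respectively).

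| | Uniform | Decay 0.7 | Decay 0.5 |
|---|---|---|---|
| SD of delay, days | 3.16 | 2.30 | 1.39 |
| Near-median cut: later group starts at day | 6 | 2 | 1 |
| Information kept, near-median cut | 75% | 59% | 51% |
| Information kept, best single cut | 75% | 71% | 68% |
| Power, exact days | 79% | 84% | 85% |
| Power, near-median cut | 69% | 62% | 59% |
| False positives, exact days | 4.8% | 4.4% | 5.3% |
| False positives, one fixed cut | 5.1% | 5.5% | 6.0% |
| False positives, cut chosen from data | 21.7% | 16.7% | 13.0% |

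The power rows compare two methods for the same effect. They do not forecast the trial's power. A ratio of 1.125 per day is exp(10 × 0.118) ≈ 3.3 over ten days, a strong modification; for a weaker one, power would be lower by either method.

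**The case against.** The strongest reply is that the plan's hypothesis is worded as a comparison of two groups, and that the trend over days is the reviewer's reading. One rationale the plan gives, that a VTE may occur before treatment begins, would fit a step or a plateau as well as a gradient. The information measure is symmetric: if the truth is a step, linear days keep only the same squared correlation with it, at best 75% in the uniform case. This stands. It makes the choice a modelling decision rather than an error to be corrected, and it is why a curved term belongs in the fix.

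The false-positive figures are also open to challenge, because they suppose that every admissible cut is tried and the best kept. A stricter limit on group size lowers them. In one early-weighted scenario (weight exp(−d/3)), looking only at cuts after day 1 or later that leave at least 25% on each side, the rate was about 8%. This stands too, and the range is therefore a worst case.

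Three stronger readings are tempting, and the documents do not support them:

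- **That the cut will be picked from the data.** The plan calls these analyses preplanned and does not say how the cut will be set.
- **That the 10-day window was accepted because the delay analysis would deal with it.** The reason given for the window is to minimise differences between hospitals; the remark on timing is a separate caveat.
- **That this analysis could show the window to be harmless.** A non-significant interaction would not show that, and the sample size was not set for one.

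**Conclusion.** The point holds as a minor improvement. The plan's only analysis of delay is a split without a cut-point, and a continuous analysis within the same test would generally serve its hypothesis better. If the effect is linear in delay, a near-median split gives up about 25–49% of the information (100% minus 75% to 51%) and about 10–27 points of power. An open cut could raise the false-positive rate to about 13–22% at worst.

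These sizes rest on the assumed delay distributions. The losses in information and power also rest on linearity; under a true step the advantage of continuous days shrinks or reverses. That an unrestricted choice of cut inflates the error rate does not depend on the shape of the effect. The primary intention-to-treat comparison and the sample size are not affected.

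**What to change.** Add to the SAP, under the delay analysis:

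- In the planned likelihood-ratio test, enter days from injury to randomisation as a continuous variable, with a main effect and an interaction with allocation.
- Prespecify a curved term, such as a restricted cubic spline, as a check on the linear form.
- Report odds ratios with 95% CIs at a few days within the well-populated range. The ends of the window may be sparse: with decay 0.7, day 10 holds about 0.009 × 1260 ≈ 11 patients, so an estimate there would be mostly extrapolation.
- If a two-group table is wanted for display, fix its cut before unblinding.
- State that time is counted to randomisation. This is a baseline value defined in both arms, whereas time to the start of IPC is not defined in controls. It also settles, for this analysis, the difference between the treatment start in the eligibility rule and the enrolment in the delay paragraph.

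The cost is a sentence or two and no extra patients. Confirm that the injury date is recorded: the eligibility rule implies it, but the documents do not list it among the baseline data. The downside is that a trend shape is assumed, which the curved term checks only in part.
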